## **15. DIRECT ACCESS TO SOURCE DATA AND DOCUMENT**

The source data is defined as all information in the original record and its approved copy with regard to the clinical findings, observations and other activities in the clinical trial, which can be used for reproduction and evaluation of clinical trial. The source documents are documents on which the source data is recorded, including printed, paper or electronic documents.

The subject's medical record and other study related documents (source documents) must be maintained and retained by the Investigator. The investigator should allow the monitors and auditors/inspectors to look up, at least including but not limited to the following information:

- Medical/physical condition of the study subject that meets the inclusion criteria prior to participating this study;
- Process of informed consent;
- Operational description of use and implantation of the study product;
- All inspection results and follow-ups;
- Examined printed output file or report (for example, X-ray film) that is dated and signed;
- Image data of Phase 2 operation;
- Description of adverse event and follow-ups of adverse event (description of event, severity, date of occurrence, duration, correlation with the study device, study procedure, outcome and treatment of adverse event, concomitant medications when an adverse event occurs);
- Description of device defect;
- Study subject's status at the end of the study or withdrawn from the study.

The sponsor expects that the appropriate study coordinator and/or investigator, appropriate source documents and appropriate environment are available for reviewing the study related documents during the period of monitoring and visit.

## **16. FINANCES AND INSURANCE**

See the relevant study contract and insurance document.

## **17. CONTENTS THAT THE CLINICAL TRIAL REPORT SHOULD COVER**

According to the regulatory requirements, the clinical trial report should be consistent with the clinical trial protocol, mainly including:

- .1. General information;

- .2. Synopsis;
- .3. Introduction;
- .4. Clinical trial objective;
- .5. Clinical trial method;
- .6. Clinical trial contents;
- .7. General clinical data;
- .8. Investigational medical device and control device or control diagnosis and treatment method;
- .9. Statistical analysis method and evaluation method used;
- .10. Clinical evaluation criteria;
- .11. Organizational structure of clinical trial;
- .12. Ethical description;
- .13. Clinical trial results;
- .14. Adverse events found in the clinical trial and their treatment;
- .15. Analysis and discussion of clinical trial results, especially the indications, scope of application, contraindications and precautions;
- .16. Conclusion of clinical trial;
- .17. Existing problems and improvement suggestion;
- .18. List of investigators;
- .19. Other conditions that need to be described.
- .20. For multicenter clinical trial, it also includes the summary of clinical trial of each sub-site

## **18. CONFIDENTIALITY**

The personal data of the subject participating in the trial is confidential; however, the Ethics Committee, food and drug administration, competent department of health and family planning or the sponsor and its authorized representative may look up the personal data of the subject participating in the trial for the demand of work according to the established procedure.

The personal data of the subject should be kept confidential during the entire period of clinical trial, and it should be ensured that the source data can be verified through the supporting information. So, a unique ID number of the subject (site number and subject number) is used to identify all data of each subject reported. If the data is kept strictly confidential and it is ensured that the privacy of the subject has been protected, the data related to this study is available for the third party (for example, under the audit of regulatory authority).

## **19. AGREEMENT ON THE PUBLICATION OF TRIAL RESULTS**

If needed, a article for multicenter trial will be prepared and published in the prestigious scientific

journal at the end of the study. No major results of experience of any individual site in this study are allowed to be published before the multicenter trial results are prepared and published. The exception from this regulation needs an prior approval from the sponsor. Other endpoints analysis specified preoperatively and non-preoperatively will be implemented in the data management department. Such secondary analysis and other proposed investigations need to be approved by the sponsor. To timely extract the statement and publish, the second publication will be entrusted to the corresponding principal authors. The final analysis and review of all multicenter trial data are required to be approved by the sponsor.

## **20. RESPONSIBILITIES THAT EACH PARTY SHOULD BEAR**

### **20.1. Responsibilities of the sponsor**

- 1) The sponsor is responsible for the initiation, application, organization and monitoring of clinical trial.
- 2) The sponsor is responsible for the organization to establish and modify the investigator's brochure, clinical trial protocol, informed consent form, Case Report Form, relevant standard operating procedure and other relevant documents, carry out the training required for the clinical trial, and provide these documents to the investigators before the study starts.
- 3) The sponsor should select the qualified trial institution and investigators.
- 4) The sponsor should sign a written agreement with the clinical trial institution and the investigator with regard to the clinical trial.
- 5) The sponsor should provide qualified study product according to the regulatory requirements. The sponsor should be responsible for the safety of investigational medical device in the clinical trial. The adverse event, serious adverse event and the device defect that may cause serious adverse event should be collected and reported in accordance with the provisions.
- 6) The sponsor should inform the regulatory authority at every level when the sponsor decides to suspend or terminate the clinical trial or at the end of the study.
- 7) The sponsor should ensure the investigator should perform the study strictly in compliance with the clinical trial protocol, timely correct the protocol deviations and reserve the rights to report to the regulatory authority.
- 8) The sponsor should bear the treatment cost and relevant economic compensation for the clinical trial-related injury or death of subjects, with the exception of damages due to the fault of medical institution and medical staff in the diagnosis and treatment.
- 9) The sponsor should select the qualified monitor for monitoring and organize the inspection appropriately.

### **20.2. Responsibilities of Clinical Trial Institution and Investigator**

- 1) The clinical trial institution should evaluate the relevant resources according to the features of investigational medical device prior to the clinical trial, so as to decide whether to perform this clinical trial.
- 2) The clinical trial institution should properly keep the records and documents of clinical trial according to the agreement with the sponsor.

- 3) Make sure that the investigators responsible for the clinical trial should have the qualification in accordance with the requirements of related laws and regulations.
- 4) The administrative department for clinical trial of medical device of clinical trial institution should cooperate with the sponsor to apply to the Ethics Committee and submit the relevant documents prior to the clinical trial according to requirements.
- 5) The investigator should ensure that the relevant workers participating in the trial have the enough resources and proper training, and keep the training related documents.
- 6) The investigator should ensure to use the investigational medical device only for the subjects of this clinical trial, and may not charge any fee.
- 7) The investigator should strictly follow the clinical trial protocol, with the exception of emergency circumstances when the subject faces the direct risk and needs immediate clinical measures, which can be reported later in a written form.
- 8) The investigator is responsible for recruiting the subjects, communicating with the subject or its legal representative before signing the informed consent.
- 9) The investigator should protect the rights, safety and health of the subjects.
- 10) In case of adverse event occurring in the clinical trial, the investigator should protect the safety of the subjects and timely report the event to the regulatory authority.
- 11) The investigator should record all adverse events occurring and device defects found in the process of clinical trial, work with the sponsor to analyze the causes of the events, form the written analysis report, present the comments on the continuation, discontinuation or termination of the trial, and report to the Ethics Committee by the administrative department for clinical trial of medical device of clinical trial institution for review.
- 12) The investigator should make sure that the clinical trial data is accurately, completely, clearly and timely recorded in the Case Report Form.
- 13) The clinical trial institution and investigator should make sure that the data, documents and records generated in the clinical trial are true, accurate, clear and safe.
- 14) The clinical trial institution and investigator should accept and cooperate with the monitoring and audit of the sponsor, the supervision of the Ethics Committee, and the inspection of the food and drug administration, competent department of health and family planning, etc., and provide all required records related to the trial.
- 15) If the clinical trial needs to be suspended or terminated, the subjects should be informed of, and it should be ensured that the subjects to receive the proper care and follow-up. The clinical trial institution and investigator should also report in accordance with the regulations, provide the detailed written explanation. Relevant report should be submitted to the local food and drug administration at the provincial, autonomous regional and municipal level if necessary.
- 16) The clinical trial institution and investigator reserve the rights to report to the regulatory authority at every level when the sponsor violates relevant laws and regulations.
- 17) The investigator should ensure to complete all records and reports at the end of clinical trial.

The investigator should also ensure that the received investigational medical devices are properly handled and recorded according to the requirements.

### **20.3. Responsibilities of other interested parties**

See the study-related contract

## **APPENDIX 2: LIST OF MODELS/SPECIFICATIONS**

M4345; M4350; M4350N

3.4.1 Adverse events	14
3.4.2 Physical examination.....	15
3.5 Analysis of Other Endpoints	15
3.5.1 Study Product Defects	15
4 Interim Analysis and Data Monitoring Committee (DMC).....	15
5 Modifications to the Original Analysis Plan	17
6 References	17
7 Appendixes.....	18
7.1 Four Abdominal Quadrants (Figure)	18

Abbreviations

Abbreviations	Full Name
AE	Adverse Event
ATC	Anatomical Therapeutic Chemical
CDC	Centers for Disease Control and Prevention
Clopper-Pearson	A method for estimating the confidence interval for a proportion with small samples based on binomial distribution
CP	Conditional power
DMC	Data Monitoring Committee
INTERCEED	Absorbable adhesion barrier
ITT	Intention-to-treat
MedDRA	Medical Dictionary for Regulatory Activities
NCI-CTCAE	National Cancer Institute-Common Terminology Criteria for Adverse Events
PP	per-protocol
PT	Preferred Term
SAP	Statistical analysis plan
SOC	System Organ Class
SSI	Incidence of surgical site infections
WHODRUG	World Health Organization Drug Dictionary

1 Introduction

This study is a prospective randomized controlled study of Johnson & Johnson Medical (Shanghai) Ltd., the primary objective is to evaluate the efficacy and safety of INTERCEED™ in reducing the incidence of adhesions at the target incision site in patients undergoing laparoscopic colorectal surgery. This Statistical Analysis Plan provides the statistical analysis methods and data processing principles with regard to effectiveness and safety.

This Statistical Analysis Plan is based on the protocol: A Prospective, Multicenter, Randomized Controlled Study to Evaluate the Effect of Absorbable Adhesion Barrier in Preventing the Abdominal Incision Site Adhesions, Version No.: 5.0 (Version Date: April 27, 2020).

1.1 Study Objectives

The primary objective of this study is to evaluate the efficacy and safety of INTERCEED™ in reducing the incidence of adhesions at the target incision site in patients undergoing laparoscopic colorectal surgery.

1.2 Study Endpoints

1.2.1 Primary Efficacy Endpoint

The proportion of subjects free of adhesions at the target incision site in each study group based on evaluation through laparoscopy at ileostomy reversal (phase 2 operation).

1.2.2 Secondary Efficacy Endpoints

- a. Extent and severity of adhesions at the target incision site and four abdominal quadrants (see Attachment 7.1)
- b. Incidence of mechanical ileus

1.2.3 Safety Endpoints

- a. Incidence of surgical site infection (SSI) at the target incision after the phase 1 operation (SSI);
- b. Incidence of all layer wound dehiscence of the target incision after Phase 1 operation;
- c. Incidence of delayed wound healing of the target incision after Phase 1 operation;
- d. Adverse events

1.2.4 Other Endpoints

Product defects of the study product

1.3 Study Design

1.3.1 Overall Design

This is a prospective randomized controlled study. The study will include 220 patients who are scheduled to undergo laparoscopic radical resection of colorectal carcinoma and ileostomy reversal in Phase 2 operation. During the Phase 1 operation, when the definite decision to create

a temporary ostomy was made, patients were randomized in 1:1 ratio to either the treatment arm (INTERCEED™) or the control arm (standard of care: no adhesion barrier, no placebo). In subjects assigned to the treatment arm, INTERCEED™ was applied beneath the target incision site (the midline incision for the removal specimen). The subjects returned 3-9 months after the phase 1 operation (colorectal carcinoma resection with temporary ileostomy) for phase 2 operation (ileostomy reversal) when the incidence, extent and severity of adhesions were evaluated through the laparoscope.. For the study schedule and events table, see [Table 1](#):

Table 1 Study Flow Chart

Item	Visit 1	Visit 2	Visit 3	Visit 4	Visit 5	Visit 6	Visit 7 ^h
Time point	Screening/Baseline: performed within 14 days before Phase 1 operation	Randomization :performed during the Phase 1 operation	Phase 1 operation	Post-Op (Phase 1) through Discharge	Phase 2 operation: performed between 3-9 months after Phase 1 operation ^a	3 days after Phase 2 operation or Discharge	6-7months after Phase 1 operation
Informed consent	X						
Demographic information	X						
Randomization		X					
Inclusion/Exclusion Criteria	X	X					
Urine/blood pregnancy test	X						
Medical/Surgical history ^b	X				X		X
Concomitant therapy ^c	X		X	X	X	X	
Physical examination ^d	X			X	X	X	
Concomitant medications ^e	X		X	X	X	X	
Procedural data ^f			X		X		
Mechanical ileus				X	X	X	X
SSI				X	X	X	X
Incision dehiscence				X	X	X	X
Delayed wound healing events				X	X	X	X
Adverse event	X	X	X	X	X	X	X
Defects of study product			X	X	X	X	X
Study completion ^g						X	X

- a. Other information except operative data should be collected from admission to hospital to the day before operation.
- b. The surgical history should be collected carefully in the three visits. The medical history at Visit 7 should be included only diagnoses potentially related to abdominal adhesions.
- c. The neoadjuvant radiotherapy information should be collected at Screening/Baseline visit, if any. The radiotherapy information includes dose and site.
- d. Including height, weight and abdominal sign.

- e. Only including the medicine related to adverse events and which is used beyond two weeks. The neoadjuvant/postoperative chemotherapy protocol and period should also be collected.
- f. The information about the procedure time, hemorrhage volume, use of sterile gloves, target incision, application of study product in the study group should be collected at the visits of Phase 1 operation; the image data and the treatment for adhesion (if any) should be collected in the Phase 2 operation.
- g. If Visit 6 occurs 6-9 months after Phase 1 operation, the study completion would be in Visit 6. If not, the study completion would be in Visit 7.
- h. Phone contact. If Visit 6 occurs 3-6 months after Phase 1 operation, the Visit 7 need to be conducted.

1.3.3 Sample Size

The relevant literature review revealed observed percentages of subjects with pelvic wall adhesions of 41% and 49.3% for INTERCEED™ and of 76% for Control [1,2]. Therefore, for the sample size determination, the assumption was conservatively made that the proportions of subjects with adhesions in INTERCEED™ and Control groups would be 0.5 and 0.75, respectively. With a one-sided significance level of 0.025, a sample size of 77 subjects in INTERCEED™ group and 77 subjects in Control group were required to achieve 90% power to detect a difference of 0.25 between the two group proportions using a one-sided Chi-square test. In order to adjust for a 30% dropout rate, a total of 110 subjects in INTERCEED™ group and 110 subjects in Control group, for a total of 220 subjects, were enrolled.

2 Basic Principles for Statistical Analysis

2.1 General Rules

Statistical analysis will be performed using SAS 9.4 or higher version statistical software. The two-sided 95% confidence interval for the proportion of subjects free of adhesions in the treatment groups will be provided by the Clopper-Pearson method. In addition, the two-sided Wald 95% confidence interval for the difference of two independent proportions (experimental group minus control group) will be constructed and used to test the null hypothesis for the superiority. If the lower limit of the confidence interval is greater than 0, it can be concluded that the experimental group is superior to the control group. Descriptive statistics will be adopted for statistical analysis, and the continuous variables will be summarized using the number of cases, mean, standard deviation, median, quartiles, maximum, and minimum; the categorical variables will be summarized using the missing value, number of cases, and percent. Unless otherwise specified, the number of subjects without missing data in the analysis set selected will be used as the denominator for percent calculation. [Table 2](#) describes the numbers of decimal places kept for the statistical parameters.

Table 2 Number of Decimal Places Reserved for the Statistical Parameters

Statistics	Number of Decimal Places Reserved
Mean, median	Keep one more decimal place than the source data, but not more than 3 decimal places
Standard deviation, 95% confidence interval	Keep two more decimal places than the source data, but not more than 3 decimal places
Maximum, minimum	Keep the same decimal place as the source data, but not more than 3 decimal places
Percent	Keep one decimal place, express the percent as “100” if it reaches a hundred percent, and express it as “0” if it is 0

P value	Keep three decimal places, and express it as P < 0.001 when all the first three decimal places are 0
---------	--

2.2 Definition of Analysis Sets

The 3 analysis sets in this study are defined as follows:

- The Intent to Treat (ITT) analysis set will include all randomized patients.
- The Per Protocol (PP) analysis set will include subjects in the ITT analysis set who did not have major protocol deviations that have a serious impact on the effectiveness and safety in patients.
- The Safety (SS) analysis set will include all subjects who have been actually treated with the study device.

The ITT and PP analysis sets should be used to analyze the primary effectiveness endpoint and secondary effectiveness endpoints. However, the primary analyses will be based on the ITT analysis set. PP analysis will be regarded as supportive analysis.

The SS analysis set will be used to analyze the safety endpoints.

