##### **2) Selection of method and time to evaluate, record and analyze the safety parameters**

The safety parameters are recorded on the e-CRF according to the investigator's record, medical record and inspection result, which are collected at each follow-up visit. The safety data is compared between groups when performing data analysis.

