## **8.9. Selection Criteria and Reason of Subjects Included in the Analysis**

All subjects that meet the inclusion/exclusion criteria are considered to meet the requirements for recruitment.

The following three analysis sets are defined in this study:

- The Intent-to-Treat (ITT) set will contain all randomized subjects.
- The Per-Protocol (PP) set will contain all subjects in the ITT set who have no major protocol deviations.
- The Safety set will contain all subjects who receive study device.

Major protocol deviations are deviations that have an impact on the primary endpoint, or that have an impact on the randomization assignment. These will be determined prior to database lock.

The primary effectiveness endpoint will be analyzed using the ITT and the PP set. However, the primary analysis will be based on the ITT set. The PP analysis will be considered supportive.

In all cases, treatment allocation will be based on randomization for the primary effectiveness endpoint using the ITT. If more than 11 subjects are mis-randomized, then an additional confirmatory analysis based on treatment received will be performed for the primary effectiveness endpoint, using the ITT.

The secondary effectiveness endpoint will be analyzed using the ITT set, while the safety endpoints will be analyzed using the Safety set.

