2.3.5 Handling of Missing Data

For the primary endpoint (presence or absence of adhesions), no imputation will be made for missing data during primary analyses. However, during the sensitivity analysis, the missing primary endpoint will be imputed by the Multiple Imputation (MI) method. When developing MI model, the following baseline variables and the variables for phase 1 operation will be used, including the subject's age, gender, randomized adhesion barrier product used during phase 1

operation, presence or absence of adhesions during phase 1 operation, duration of phase 1 operation, blood loss and incision length, and radiotherapy or chemotherapy used at baseline or not.

The secondary endpoint will be analyzed based on the ITT set. No imputation will be made for missing data. All secondary study endpoints will be analyzed using available data.

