3.3.2 Secondary Effectiveness Endpoint Analysis

The secondary effectiveness endpoints will be summarized based on the SS analysis set.

The incidence of mechanical ileus in subjects will be descriptively summarized per treatment group using the number of cases (percentage). The incidence of ileus will be compared between groups using the chi-square test, with the P-value calculated. The two-sided 95% confidence interval for the proportion of subjects with mechanical ileus in the treatment groups will be provided by the Clopper-Pearson method. In addition, the two-sided Wald 95% confidence interval for the difference of two independent proportions (experimental group minus control group) will be constructed.

The extent (no adhesions, grades 1, 2, 3) and severity (no adhesions, grades 1, 2, 3) of adhesions at the target surgical incision site and four abdominal quadrants observed during the phase 2 operation will be descriptively summarized per treatment group using the number of cases (percentage).

In addition, the extent and severity of adhesions at the target incision will be compared between groups using MH (Mantel - Haenszel) chi-square test, with the P-value calculated.

```
proc freq data=data;  
  tables treat*response / chisq cmh nocol nopct;  
  weight count;  
run;
```

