3.4 Safety Analysis

All safety analyses will be based on the SS analysis set. A summary will be made per treatment group, and treatment grouping will be made according to subject's actual treatment. The safety analyses include:

- Incidence of surgical site infection (SSI) at the target incision after the phase 1 operation;
- Incidence of full-thickness disruption of target incision after the phase 1 operation;
- Incidence of wound healing delayed event at the target incision after the phase 1 operation;
- Adverse events
- Physical examination

The incidences of SSI/full-thickness disruption/wound healing delayed event at the target incision after the phase 1 operation will be descriptively summarized using the number of cases (percentage), and the 95% CI for each event will be provided per treatment group using the Clopper-Pearson method; in addition, the two-sided Wald 95% confidence interval for the difference in proportion of subjects of each event between treatment groups (experimental group minus control group) will be constructed.

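### The Safety set admits only subjects given the device, so the no-barrier control arm drops out of every comparison run on that set

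*SAP*

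**What the plan says.** **Definition of the set.** SAP 2.2: "The Safety (SS) analysis set will include all subjects who have been actually treated with the study device". Protocol 8.9 agrees: "The Safety set will contain all subjects who receive study device".

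**What controls receive.** SAP 1.3.1 describes "the control arm (standard of care: no adhesion barrier, no placebo"; the Protocol synopsis says the same.

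**What is run on the set.** SAP 3.4: "All safety analyses will be based on the SS analysis set". That section asks for summaries by treatment group according to actual treatment. For surgical site infection, dehiscence and delayed healing it adds "the two-sided Wald 95% confidence interval for the difference in proportion of subjects of each event between treatment groups", taken as experimental minus control. Protocol 7.1.7 states: "The safety data is compared between groups when performing data analysis". Protocol 8.1 asks for safety summaries by treatment group on the Safety set. SAP 3.1.4 (medical history), 3.1.5 (medications) and 3.2.1 (Phase 1 surgical data) use the same set.

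**Secondary effectiveness.** SAP 3.3.2: "The secondary effectiveness endpoints will be summarized based on the SS analysis set". It then specifies a chi-square test and a difference interval for ileus, and Mantel-Haenszel tests for extent and severity at the target incision. SAP 2.3.5 says instead: "The secondary endpoint will be analyzed based on the ITT set". Protocol 8.1 and 8.9 also name ITT, and SAP 2.2 names ITT and PP. SAP section 5 declares no modification to the original plan.

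**The concern.** A set defined by receipt of the device cannot hold the arm that receives none. Every comparison assigned to it then lacks its comparator. Safety is part of the stated primary objective, and the trial is meant to support registration. Wound infection, dehiscence and delayed healing can all follow the colorectal operation itself, so rates in the INTERCEED arm alone cannot separate the effect of the barrier from that of the surgery.

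SAP 3.3.2 carries the same defect into the secondary effectiveness endpoints and contradicts four other places in the two documents. Even with a corrected Safety set, the SAP would still name two populations for those endpoints, one of them grouped by treatment received rather than as randomised.

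**Working it through.** **1. Arm sizes in the plan.** Inputs from SAP 1.3.3: adhesion rates 0.50 and 0.75, one-sided alpha 0.025, power 90%, dropout 30%. With the pooled-variance formula and no continuity correction:

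n = [1.96·√(2·0.625·0.375) + 1.2816·√(0.50·0.50 + 0.75·0.25)]² / 0.25² = (1.342 + 0.848)² / 0.0625 ≈ 76.7, rounded up to 77 per arm.

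77 / (1 − 0.30) = 110 per arm, 220 in total. The plan's figures reproduce; they serve here only as denominators.

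**2. Who is in the Safety set.** Apply the definition and the actual-treatment grouping of SAP 3.4 to each possible case:

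| Randomised to | Received | In Safety set as written? | Column |
|---|---|---|---|
| INTERCEED | INTERCEED | Yes | INTERCEED |
| INTERCEED | No barrier | No | – |
| Control | No barrier | No | – |
| Control | INTERCEED in error | Yes | INTERCEED |

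The control column is empty in every case, so allocation errors cannot fill it. With all subjects treated as assigned, the set is at most 110 INTERCEED and 0 control.

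**3. Wald interval for a difference.** The half-width is 1.96·√[p₁(1 − p₁)/n₁ + p₂(1 − p₂)/n₂]. With n₂ = 0, both the control proportion and the second variance term divide by zero. The intervals for infection, dehiscence and delayed healing are undefined, as is the ileus interval in SAP 3.3.2.

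**4. Chi-square and Mantel-Haenszel tests.** With an empty control row, the expected counts in that row are zero. Only one row is left, so the degrees of freedom are (1 − 1)(2 − 1) = 0 for ileus. The extent and severity tests also have a single treatment group, so there is nothing to compare.

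**5. Population named for secondary effectiveness.**

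| Place | Set |
|---|---|
| Protocol 8.1 | ITT |
| Protocol 8.9 | ITT |
| SAP 2.2 | ITT and PP |
| SAP 2.3.5 | ITT |
| SAP 3.3.2 | Safety set |

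**6. What a corrected set would give.** With 110 per arm and a common event rate p, the half-width is 1.96·√[2p(1 − p)/110]. The documents give no event rates, so the rates below are assumptions.

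| Assumed p | Half-width (percentage points) |
|---|---|
| 2% | 3.7 |
| 5% | 5.8 |
| 10% | 7.9 |
| 20% | 10.6 |

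**The case against.** The strongest reply is that this is a badly worded definition, not a decision to leave controls out. The section that names the Safety set also asks for results by group and for experimental-minus-control intervals, and Protocol 7.1.7 and 8.1 expect safety results by group. The visit schedule collects adverse events and wound outcomes without distinction by arm, so no data are lost. For secondary effectiveness, four places say ITT and one says otherwise, which looks like a stray label; under the other four the tests can be run. The primary analysis is untouched, and no decision rule is attached to the safety intervals.

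Much of this stands. The intent to include controls is clear, and the effectiveness problem arises only through SAP 3.3.2. The adverse event tables could still be filled for INTERCEED, so only the between-group intervals and tests are strictly undefined. The figure of 110 is an upper bound. Bias from selecting by device use is not an added harm of the present text, which leaves no comparison to bias; it would arise only if effectiveness were analysed on an as-treated set that included controls.

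Intent does not, however, supply the missing rule. The same restriction stands in both documents, and neither says which controls qualify. Unless that is written down first, the denominator of every safety result is chosen after the data exist.

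**Conclusion.** The point holds. As written, the Safety set contains no control subjects, and it contradicts the comparative analyses it governs. The three safety difference intervals are undefined. So are the ileus chi-square test and interval and the two Mantel-Haenszel tests if SAP 3.3.2 is followed. The adverse event, medical history, medication and Phase 1 surgical tables would describe INTERCEED subjects only. SAP 3.3.2 also conflicts with four other statements of the population for the secondary effectiveness endpoints.

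The zero follows from the definitions and rests on no assumed rate. The upper bound of 110 assumes full enrolment and device use in every INTERCEED subject. The primary ITT and PP analyses are not affected. Because safety is part of the primary objective, this must be corrected before database lock.

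**What to change.** 1. **Protocol 8.9 and SAP 2.2:** define the Safety set as all randomised subjects who underwent the Phase 1 operation, grouped by treatment actually received (INTERCEED or no barrier). This matches the grouping rule already in SAP 3.4 and gives up to 110 + 110 = 220 subjects. Since randomisation takes place during that operation, the set should be essentially all randomised subjects and differ from ITT mainly in how they are grouped.
2. **SAP 3.3.2:** replace the Safety set with ITT, with PP as supportive. PP is named for these endpoints in SAP 2.2 but not in SAP 2.3.5 or Protocol 8.1 and 8.9, so those places should be aligned, or the addition declared in SAP section 5.

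The core change is one sentence in the protocol and two in the SAP. No new data are needed, and the sample size and primary analysis do not change.
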